## **Vernakalant IV Sterile Concentrate Prospective Safety Registry Study**

Sponsor Protocol Identifier: 6621-049-00

3 August 2016

---

selected retrospectively and prospectively are selected in the same manner. This will minimize the risk of any potential selection bias.

Missing data is always a concern; and including patients retrospectively could increase the amount of missing data. However the impact of missing data on the evaluation of the HOIs and other rare events is not anticipated to be a concern as this information is routinely collected in the patient's hospital record. Therefore these event rates at the completion of the study would not be biased downward. Further, any possible observer bias by selecting patients retrospectively will be minimised by only including patients with the key data variables as stipulated in section 7.2.1 and the assessment of whether an event is characterized as an HOI is adjudicated by an independent Safety Review Committee (SRC).

### **Informed consent**

Patients who fulfil the criteria above will be contacted either at clinic during their next routine follow up cardiology appointment, or by phone and / or mail. The approved informed consent form will then be discussed in detail with the patient and if they agree to take part, the patient will personally sign and date the consent form.

If local regulations permit, sites may also ask their IEC for an informed consent waiver.

### **Identification of retrospective patients**

As soon as local regulatory and Ethics Committee approval are obtained (where applicable) sites will be able to enrol retrospective patients concurrently with prospective patients.

Strategies for identifying retrospective patients will vary between sites as a result of varying staff availability and record keeping. Sites with searchable electronic patient records for example will find it easier to identify patients than sites without.

Several methods will be employed to identify retrospective patients who have been treated with Brinavess since April 2013.

1. Patients will be approached at their routine clinic visit. If a study team member notices during this visit that Brinavess treatment has been previously given, the study will be discussed with the patient at this time and asked if they are willing to give their consent to take part.
2. Following a search of the hospital records,
  - a. Identified patients will receive a telephone call, the study discussed with them and at their next routine visit asked if they are willing to give their consent to take part. OR
  - b. Identified patients will receive a telephone call, the study discussed with them, information mailed to the patient and then the patient will be asked to sign and mail back the completed consent form. OR

## **Vernakalant IV Sterile Concentrate Prospective Safety Registry Study**

Sponsor Protocol Identifier: 6621-049-00

3 August 2016

---

- c. Identified patients will receive a letter with information regarding the study and if willing to take part, sign the consent form at their next routine visit. OR
- d. Identified patients will receive a letter with information regarding the study and if willing to take part, sign and mail back the completed consent form.

Example letters that the site may wish to use can be found in Appendix II. These letters will be sent by the study coordinator or Investigator to the patient. To maintain patient confidentiality copies of the letters sent will not be seen by, or provided to, the Sponsor.

### **7.2.1 Required key data elements for retrospective data collection**

The data elements listed in section 7.1.1 will be collected for all patients enrolled retrospectively, with the exception of the following which may not be available retrospectively in the patients' hospital records;

#### **Patient demographics**

- Height

#### **Presenting medical conditions**

- NYHA heart failure class

Where NYHA class is not routinely recorded in the patients' hospital records, as the NYHA classification system is based on patients' symptoms, where possible the investigator should classify this retrospectively as any severe symptoms will be documented. Patient eligibility is expected to follow hospital's standard procedures and SmPC guidelines.

#### **Other medical and lifestyle history**

- Smoking

#### **Dosing/administration of vernakalant IV**

- Stop time for each infusion
- Time to conversion

The total infusion time is expected to follow both SmPC and hospital guidelines.

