**Vernakalant IV Sterile Concentrate Prospective Safety Registry Study**

Sponsor Protocol Identifier: 6621-049-00

3 August 2016

---

- Liver function tests and other analytes (e.g., platelets) required for estimation of liver function using established algorithms
- **Medical history**
  - History of heart failure (year of diagnosis)
    - Prior hospitalisations for acute heart failure (most recent, number in last 6 months)
    - Previously documented left ventricular ejection fraction (most recent)
  - History of AF
    - Year of initial diagnosis
    - Classification (first onset, paroxysmal, persistent, permanent, post-operative, Wolff-Parkinson-White, other?)
  - Pacemaker (yes/no, year implanted)
  - Implantable cardioverter defibrillator (ICD) (yes/no, year implanted)
  - History of cardiovascular disease
    - Valvular heart disease
    - Clinically meaningful valvular stenosis
    - Hypertrophic obstructive myopathy
    - Restrictive cardiomyopathy
    - Constrictive pericarditis
    - MI, angina, stroke, ACS, vascular surgery (stent, coronary artery bypass graft, etc.)
    - Hypertension
  - **Other medical and lifestyle history**
    - Diabetes
    - Smoking
    - Hyperlipidemia/ hypercholesterolemia
- **Dosing/Administration of vernakalant IV**
  - Total number of infusions during treatment episode
  - Total dose with each infusion
  - Start/stop times for each infusion
  - Amount of time between each infusion
  - Time to successful conversion
- **Methods of site monitoring of patients during and following each vernakalant infusion per SmPC guidance**

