### **11.2 Source Documents**

The physician should maintain source documents for each patient enrolled in the study. Source documents include patient charts, doctors' notes, study-specific supplementation data collection forms, ECG tracings (including conversion to sinus rhythm ECGs within 90 minutes of vernakalant IV treatment), lab results slips, supportive documentation of all HOIs and SAEs, and worksheets designed to collect the data to be entered in the CRF and will be kept as part of the patients' medical records. Baseline ECG tracings recorded as part of standard of care during the index hospitalization and prior to vernakalant administration and ECGs corresponding to arrhythmic HOIs and SAEs during the follow-up period may also be requested.

Data recorded into the e-CRF should also be downloaded and stored on local computers at the site. Should this not be possible sites will print a date-stamped version of the completed CRF for each patient to be signed by the study physician and stored in files at the site.

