3.4 Derived Variable Definitions

The following derived/calculated values will be used:

- Age at enrolment = [(date of informed consent – date of birth) + 1]/365.25, or self-reported age if date of birth is not available.
- BMI = Weight (Kg)/Height (m)². English standard units should be converted to international or metric units.
- (S)AE or HOI onset in days and time (in hours or minutes) following vernakalant IV infusion = date/time of onset or (S)AE-date – date/time of start of first infusion.
- Duration or period = (stop time – start time). Note there are key durations that include, but are not limited to, duration of vernakalant IV infusions and duration of HOI and SAE.
- Vernakalant IV dose per body weight = vernakalant IV dose (mg) / body weight (kg).
- Duration of time to conversion to sinus rhythm = (date/time of conversion to sinus rhythm – date/time of start of first infusion).
- Percentage of weight-based dosing recommendation per label (%) = (Vernakalant IV dose [mg/kg] / Recommended vernakalant IV dose [mg/kg]) * 100. Range from 0% to above 100%, with 100% indicating that dose is equal to recommended dose, calculated per first or second infusion. Patients with cumulative doses greater than the maximum recommended dose will be noted (overall and for first and second infusion, separately).
- Duration of current AF in hours = (Vernakalant administration date/time - AF onset date/time).

- Time since first AF diagnosis = (Start date of Vernakalant IV administration - Date of first AF diagnosis).
- Rate of conversion to sinus rhythm for at least one minute within 90 minutes of start of first vernakalant IV administration = (Number of relevant patients converted to sinus rhythm for at least one minute within 90 minutes of start of first vernakalant IV administration) / (Total number of relevant patients administered vernakalant IV). Rate of conversion can be evaluated based on different types of patients, e.g. all patients receiving vernakalant IV or all such patients with other restrictions.
- Elevated liver enzymes (inclusive of possible abnormal liver function or liver injury) = an increase above upper limit of normal (ULN) for alanine aminotransferase (ALT), aspartate aminotransferase (AST), or total bilirubin (TB) or conjugated bilirubin. [1,2]
- Total hospital length of stay (hours) = (Date/time of discharge or release of facility – Date/time of hospital admission).

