4.4 Handling Withdrawals and Missing Data

There will be no imputation of missing data. Data will be presented and summarised as it was recorded. Reasonable attempts should be made by the treating physician and/or site personnel to limit the amount of missing data. The proportion of missing data is expected to be low for this study, especially with regard to the details of administration of vernakalant IV and concomitant therapies, collected laboratory values, and occurrence of HOIs during the brief, in-hospital follow-up period. Reasonable attempts will be made to limit the amount of missing medical history and presenting condition data to ensure that important information is captured.

Prospective supplemental data collection of study-specific data elements, such as patient's weight, heart failure NYHA functional class, vernakalant administration and patient monitoring is expected to limit missing data.

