| Flecainide | xx (xx.x%) | xx (xx.x%) | xx (xx.x%) | xx (xx.x%) | xx (%) |
| <Other class I medications, if used> | | | | | |

| Characteristic | Within 4 hours prior to the start of first vernakalant infusion ^{1,2} | Within 4 hours subsequent to the start of first vernakalant infusion ^{1,2} | Within 90 minutes subsequent to the start of first vernakalant infusion ^{1,2} | Any time during the hospitalisation/medical encounter (but not within 4 hours prior or subsequent to the start of first vernakalant infusion) ^{1,2} | Overall |
|--|---|--|---|---|---------|
| Class III | | | | | |
| Amiodarone | xx (xx.x%) | xx (xx.x%) | xx (xx.x%) | xx (xx.x%) | xx (%) |
| Ibutilide | xx (xx.x%) | xx (xx.x%) | xx (xx.x%) | xx (xx.x%) | xx (%) |
| Sotalol | xx (xx.x%) | xx (xx.x%) | xx (xx.x%) | xx (xx.x%) | xx (%) |
| < Other class III medications, if used > | xx (xx.x%) | xx (xx.x%) | xx (xx.x%) | xx (xx.x%) | xx (%) |
| Missing | xx | xx | xx | xx | |

Note: Total n for each variable includes non-missing observations. Percentages, where applicable, are calculated with non-missing observations in denominator unless otherwise noted.

¹ Includes patients administered IV anti-arrythmic agents for pharmacological cardioversion during the specified time during the hospitalisation/medical encounter. First column includes administration within 4 hours prior to the start of first vernakalant infusion. Second column includes administration within 4 hours subsequent to the start of first vernakalant infusion. Third column includes administration NOT within 4 hours prior and/or subsequent to the start of first vernakalant infusion.

² Retrospective patients may have missing vernakalant administration date/time.

³ Percentages based on number of IV AA administrations

⁴ Based on the ATC classification, except for sotalol. For the purposes of this study, study programmers manually reclassified sotalol from ATC code C07AA (Beta Blocking Agents, Non-Selective) to ATC Code C01BD (Antiarrhythmics, Class III) in the analysis datasets as consistent with the Vaughan Williams Classification of Antiarrhythmic Drugs detailed in the SAP.

Template of Table 12a.1 will be applied to the following two tables. Please note: for Table 12a.2, footnote 2 does NOT apply , and all subsequent footnote numbers should be adjusted correspondingly.

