¹ Includes patients who receive more than 1 infusion within a single treatment episode.

² Rate of conversion (%) is calculated as: (number of patients who have conversion to sinus rhythm for at least one minute with 90 minutes after first vernakalant infusion within effectiveness analysis population) / (total number of patients within effectiveness analysis population) x 100.

³ Rate of conversion (%) is calculated as: (number of patients who, within 90 minutes after first vernakalant infusion, have conversion to sinus rhythm for at least one minute but have no ECV or IV Class I/III AA within overall analysis population) / (total number of patients within overall analysis population).

⁴ Rate of conversion (%) is calculated as: (number of patients who, within 90 minutes after first vernakalant infusion, have conversion to sinus rhythm for at least one minute but have no ECV, oral propafenone/flecainide or IV Class I/III AA within overall analysis population) / (total number of patients within overall analysis population).

Template of Table 15a will be applied to the following three tables.

Table 15b Proportion of Patients Converted to Sinus Rhythm and Time to Conversion Following Vernakalant Infusion (SmPC Subgroup Analysis)

Table 15c Proportion of Patients Converted to Sinus Rhythm and Time to Conversion Following Vernakalant Infusion (Non-Surgery Patients)

Table 15d Proportion of Patients Converted to Sinus Rhythm and Time to Conversion Following Vernakalant Infusion (Post-Cardiac Surgery Patients)

Table 16.1a.1 Serious Adverse Events (System Organ Class and Preferred Term) by Outcome (Analysis Set) – Investigator Assessment

| | Analysis Set (N=xxx) Outcome | | | | | | | |
|---|---|----------|---|----------|---|----------|---|----------|
| | Recovered | | Recovered with Sequelae | | Not Recovered | | Overall | |
| System Organ Class/ High Level Term/ Preferred Term | Patients n (Cumulative Incidence ¹) | Events n | Patients n (Cumulative Incidence ¹) | Events n | Patients n (Cumulative Incidence ¹) | Events n | Patients n (Cumulative Incidence ¹) | Events n |
| Any SAE | xx (x.x%) | xx |
| SOC 1 | xx (x.x%) | xx |
| HLT 1 | xx (x.x%) | xx |
| PT 1 | xx (x.x%) | xx |
| PT 2 | xx (x.x%) | xx |
| SOC 2 | xx (x.x%) | xx |
| HLT 2 | xx (x.x%) | xx |
| PT 1 | xx (x.x%) | xx |
| PT 2 | xx (x.x%) | xx |

Note: SAE events include reported HOIs that are mapped to specific MedDRA terms.

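### The 90-minute conversion rate scores patients of unknown timing as non-converters, to the extent that status depends on a time that retrospective records may lack

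*Protocol*

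**What the plan says.** The effectiveness endpoint is conversion to sinus rhythm for at least one minute within 90 minutes of the start of the first administration (Protocol 9.1; SAP 3.3).

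- **Data collected.** The key data elements in Protocol 7.1.1 contain one conversion item, "Time to successful conversion". No separate yes/no item for conversion within 90 minutes is listed. Protocol 11.2 names ECG tracings among the source documents, "including conversion to sinus rhythm ECGs within 90 minutes of vernakalant IV treatment".
- **Retrospective patients.** Protocol 7.2.1 asks for the 7.1.1 elements "with the exception of the following which may not be available retrospectively". The exempt items under dosing and administration are the infusion stop time and "Time to conversion". Footnotes to SAP Tables 7.1, 12a.1, 12b.1, 13a.1 and 13b.1 add: "Retrospective patients may have missing vernakalant administration date/time".
- **Denominator.** SAP 3.4 divides by "Total number of relevant patients administered vernakalant IV". Table 15a footnote 2 divides by "total number of patients within effectiveness analysis population", and footnotes 3 and 4 divide by the whole overall analysis population. The general note under the same table instead bases percentages on non-missing observations unless otherwise noted.
- **Missing data.** SAP 4.4: "There will be no imputation of missing data".

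Neither document says how 90-minute status is assigned when the conversion time or the infusion time is missing.

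**The concern.** Placing a conversion inside or outside 90 minutes normally takes two clock times: the start of the first infusion and the moment of conversion. The plan allows the second to be absent for retrospective patients, and the SAP expects that the first sometimes will be. A patient known to have converted, but at an unknown time, cannot be placed in the numerator from the recorded time. Under the footnote denominators that patient still counts below the line, so the arithmetic effect is that of a non-converter.

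The missing times should fall mainly in one enrolment group. A lower retrospective rate could therefore reflect record-keeping and be read as lower effectiveness, and the pooled rate would carry part of the same deficit. Protocol 7.2 concedes that retrospective inclusion could increase missing data, but its reassurance covers the HOIs and other rare events, not conversion.

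The Table 15a rate blocks print only n and the number converted. They have no row for unknown status. The SAP handles a comparable gap explicitly elsewhere: Table 11 footnote 4 classes anti-arrhythmic use with missing times as unknown.

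**Working it through.** **Inputs**

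- Retrospective patients, R = 435 (Protocol Appendix I). The country rows reproduce the totals: prospective 110 + 15 + 55 + 60 + 35 + 100 = 375; retrospective 0 + 0 + 0 + 20 + 70 + 345 = 435; 375 + 435 = 810, as stated.
- Target N = 2,000, so 2,000 − 435 = 1,565 are taken as prospective. This treats everyone enrolled before the Appendix I forecast as prospective. The retrospective share is 435/2,000 = 0.2175.
- True 90-minute rate p = 0.511, the phase III figure in the Protocol background, assumed equal in both groups.
- m = share of retrospective converters whose 90-minute status cannot be set. The documents give no figure. I **assume** 10, 25 and 50%.

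The plan states no precision for the conversion rate, so there is no planned figure to reproduce for it.

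**A. Full denominator (SAP 3.4; Table 15a footnotes 2 to 4), unknown status not in the numerator**

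- Retrospective rate = p(1 − m)
- Pooled rate = [1,565p + 435p(1 − m)] / 2,000 = p(1 − 0.2175m)

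| m | Converters affected (435 × 0.511 × m) | Retrospective | Pooled |
|---|---|---|---|
| 10% | 22 | 0.511 × 0.90 = 46.0% | 0.511 × 0.97825 = 50.0% |
| 25% | 56 | 0.511 × 0.75 = 38.3% | 0.511 × 0.945625 = 48.3% |
| 50% | 111 | 0.511 × 0.50 = 25.6% | 0.511 × 0.89125 = 45.5% |

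**B. Non-missing denominator (Table 15a general note), untimed converters dropped above and below the line**

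- Retrospective rate = p(1 − m) / (1 − pm)
- m = 10%: 0.4599 / 0.9489 = 48.5%
- m = 25%: 0.38325 / 0.87225 = 43.9%
- m = 50%: 0.2555 / 0.7445 = 34.3%

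B removes only successes and keeps every non-converter, so it is still biased down. A and B also show that the note and the footnotes lead to different printed rates from the same data.

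**C. Bounds on the full denominator.** Counting no unknown-time converter as within 90 minutes gives the figures in A. Counting all of them gives 51.1% in this illustration. The interval from A to 51.1% is therefore 5.1, 12.8 or 25.6 points wide for the retrospective column and 1.1, 2.8 or 5.6 points wide for the pooled column.

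**D. Status captured independently of the time.** m = 0, and the bias is zero.

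**The case against.** The strongest reply is that status and time are different things. Protocol 7.2.1 exempts the time, not the fact of conversion within 90 minutes. The time-to-conversion block of Table 15a is restricted to patients already classed as 90-minute converters, yet it has a row for missing times, so the shell allows a responder with no recorded time. The source ECGs in Protocol 11.2 offer another route to status. A reader might infer that the plan scores every untimed converter as a failure. No passage says so, and this reply stands against that inference. It does not close the gap, because 7.1.1 lists only the time and no rule says that status will be set from ECGs.

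Other replies hold in part:

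- *The general note calls for non-missing denominators.* It does, but footnotes 2 to 4 can be read as its stated exception. The conflict needs settling, and working B shows that following the note does not remove the bias.
- *Infusion start time is not exempt.* Correct: only the stop time is listed in 7.2.1. The SAP footnotes expect missing administration times all the same, without saying how many.
- *The missingness will be visible.* Table 15a has separate prospective and retrospective columns, and Table 18 counts missing time to cardioversion by enrolment method. But Table 18 counts over all patients, so the number of untimed converters cannot be read from it. The rate without time restriction promised in SAP 3.3 and 5.10 has no row in Table 15a.
- *The net direction is not fixed.* The effectiveness population excludes patients given other cardioversion within 90 minutes, which also needs clock times. An untimed electrical cardioversion could be credited as a conversion and push the rate up. The downward bias described here is that of the denominator rule alone.
- *The pooled effect may be small.* At m = 10% the shift is 1.1 points, against an exact 95% interval of 48.9 to 53.3% at 51.1% and N = 2,000, a half-width of about 2.2 points.

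**Conclusion.** The point holds in conditional form. The full-population denominator is a stated rule, it comes with no imputation, and the plan itself allows the timing data to be absent for one enrolment group. Wherever 90-minute status cannot be set, the patient is counted as a non-converter and the rate is pulled down by the factor (1 − m) in the retrospective column and (1 − 0.2175m) in the pooled one.

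The size is not established. The figures rest on an assumed m, a 51.1% rate borrowed from phase III, and an enrolment forecast of 435. They show sensitivity and are not a prediction. It would go too far to conclude that the reported rates will be wrong by these amounts, or that the prospective column must become the primary result: Protocol 9.1 defines the endpoint on all patients, and nothing here requires changing that.

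The effect is confined to secondary objective 4, which is descriptive. The HOI analyses do not use conversion time.

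**What to change.** In SAP 3.4, 5.10 and Tables 15a to 15d:

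1. State that 90-minute status is set from any available source, either the recorded time or a conversion ECG.
2. Add a row for patients who converted at an unknown time.
3. Report the retrospective and pooled rates on the full denominator as two bounds: no unknown-time converter counted as within 90 minutes, then all of them.
4. Reconcile the general note under Table 15a with footnotes 2 to 4.
5. Add the row for conversion without time restriction that SAP 5.10 already promises.

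Do not drop untimed converters from numerator and denominator, for the reason shown in working B. Keep the existing prospective and retrospective columns, without redefining which is primary.

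The cost is some SAP wording and a few table rows. The downside is a range in place of a single figure in the retrospective and pooled columns.
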